2.1 Primary objectives

- **Induction Therapy - Part A:** To determine the safety and tolerability of administration of multiple ascending doses of KHK4083 and to select the highest dose tolerated by subjects with moderately active UC to recommend for use in Part B;

	Forms			
	Title	Statistical Analysis Plan Template		
	Code	Version	Effective Date	Page
	FRM_ST03_032	01	23 Apr 2015	9 of 53

- **Induction Therapy - Part B:** To determine if the recommended dose of KHK4083 identified in Part A improves the mucosa in subjects with moderately active UC at Week 12 as measured by the modified Mayo endoscopy subscore (mMES).

2.2 Secondary objectives

- To determine if KHK4083 at dose levels different than the recommended dose improve the mucosa based on the mMES;
- To determine if any dose level of KHK4083 administered as Induction Therapy will meet the following objectives at Week 12:
 - Improve the mucosa based on the modified Baron endoscopic score;
 - Improve the mucosa based on the Ulcerative Colitis Endoscopic Index of Severity (UCEIS);
 - Induce mucosal healing based on the mMES;
 - Improve clinical signs and symptoms based on total Mayo Clinic score;
 - Improve clinical signs and symptoms based on partial Mayo Clinic scores (Week 2 through Week 12, excludes endoscopy subscores);
 - Induce a clinical response based on a reduction in the total Mayo Clinic score (i.e., reduction of at least 3 points and a decrease of at least 30% from Baseline [Week 0] to Week 12) and rectal bleeding subscale (i.e., reduction of at least 1 point from Baseline [Week 0] to Week 12) (or a defined absolute rectal bleeding score of 0 or 1 at Week 12);
 - Induce clinical remission based on a total Mayo Clinic score (i.e., score of ≤ 2) and subscores (i.e., no subscores > 1).
- To characterize the PK of KHK4083 in subjects with moderately active UC following multiple dose administration;
- To evaluate the development of antibodies against KHK4083 (immunogenicity).

2.3 Exploratory objectives

- To determine if multiple doses of KHK4083 administered during Open-label Extension (OLE) or Long-term Extension (LTE) Therapy will meet the following objectives at Week 52 (or as noted) when compared with Baseline (Week 0) scores (or subscores) or assessments:
 - Improve clinical signs and symptoms based on total Mayo Clinic score;
 - Improve clinical signs and symptoms based on partial Mayo Clinic scores (excludes endoscopy subscores) at Week 16 through Week 52, and the OLE/LTE Therapy Follow-up Period (Week 56 through Week 64);
 - Induce a clinical response based on a reduction in the total Mayo Clinic score and rectal bleeding subscale (or a defined absolute rectal bleeding score);
 - Induce clinical remission based on a total Mayo Clinic score and subscores;
 - Induce durable clinical responses and durable clinical remissions (present at both Weeks 12 and 52), and glucocorticoid-free clinical remission;
 - Induce mucosal healing based on the mMES;

	Forms			
	Title	Statistical Analysis Plan Template		
	Code	Version	Effective Date	Page
	FRM_ST03_032	01	23 Apr 2015	10 of 53

- Improve the mucosa based on the mMES, UCEIS, and/or modified Baron endoscopic score;
 - Induce a remission (Week 12; Week 52) based on modified Mayo endoscopy, stool frequency, and rectal bleeding subscores (defined as an mMES of 0 or 1, stool frequency subscore of 0 or 1, and rectal bleeding subscore of 0).
- To evaluate the activity of KHK4083 on health-related quality of life (HRQL), which will be based on the subject's completed Inflammatory Bowel Disease Questionnaires (IBDQs) in comparison to Baseline assessments;
 - To measure changes from Baseline in corticosteroid (glucocorticoid) dosages;
 - To determine the percentage of subjects who are glucocorticoid-free from Week 16 through Week 52, and through the OLE/LTE Therapy Follow-up Period (Week 56 through Week 64);
 - To evaluate the pharmacodynamic (PD) profile of KHK4083;
 - To explore the PK-PD relationships.

3. Study Design

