 - Induce clinical remission based on a total Mayo Clinic score (i.e., score of ≤ 2) and subscores (i.e., no subscores > 1).
 - To characterize the PK of KHK4083 in subjects with moderately active UC following multiple dose administration;
 - To evaluate the development of antibodies against KHK4083 (immunogenicity).
- Refer to Section 10.2 for additional details on all secondary endpoints.

Exploratory:

- To determine if multiple doses of KHK4083 administered during the Open-label Extension (OLE) / Long-term Extension (LTE) Therapy phase will meet the following objectives at Week 52 (or as noted) when compared with Baseline (Week 0) scores (or subscores) or assessments:
 - Improve clinical signs and symptoms based on total Mayo Clinic score;
 - Improve clinical signs and symptoms based on partial Mayo Clinic scores (excludes endoscopy subscores) at Week 16 through Week 52, and the LTE Therapy Follow-up Period (Week 56 through Week 64);
 - Induce a clinical response based on a reduction in the total Mayo Clinic score and rectal bleeding subscale (or a defined absolute rectal bleeding score);
 - Induce clinical remission based on a total Mayo Clinic score and subscores;
 - Induce durable clinical responses and durable clinical remissions (present at both Weeks 12 and 52), and glucocorticoid-free clinical remission;
 - Induce mucosal healing based on the mMES;
 - Improve the mucosa based on the mMES, UCEIS, and/or modified Baron endoscopic score;

- Induce remission (Week 12; Week 52) based on modified Mayo endoscopy, stool frequency, and rectal bleeding subscores (defined as an mMES of 0 or 1, stool frequency subscore of 0 or 1, and rectal bleeding subscore of 0);
- To evaluate the activity of KHK4083 on health-related quality of life (HRQL), which will be based on the subject's completed Inflammatory Bowel Disease Questionnaires (IBDQs) in comparison to Baseline assessments;
- To measure changes from Baseline in corticosteroid (glucocorticoid) dosages;
- To determine the percentage of subjects who are glucocorticoid-free from Week 16 through Week 52, and through the OLE/LTE Therapy Follow-up Period (Week 56 through Week 64);
- To evaluate the pharmacodynamic (PD) profile of KHK4083;
- To explore the PK-PD relationships.

Refer to Section 10.3 for additional details on exploratory endpoints.

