10.3 Exploratory Endpoints

Efficacy and PD exploratory endpoints will be included in this study for all subjects with moderately active UC who receive both Induction Therapy and OLE/LTE Maintenance Therapy. The exploratory endpoints for all subjects who receive both Induction Therapy and OLE/LTE Maintenance Therapy are as follows:

- Clinical improvement at Week 52;
Improvement will be based on a reduction (mean change from Baseline [Week 0] to Week 52) in the total Mayo Clinic score (0 to 12).
- Clinical improvement at Weeks 16, 20, 24, 28, 32, 36, 40, 44, 48, and 52 and at OLE/LTE Therapy Follow-up Period visits (Weeks 56, 60, and 64);
Improvement will be based on mean changes from Baseline (Week 0) in the partial (excludes endoscopy subscores) Mayo Clinic score (0 to 10).

- Clinical response at Week 52;
A clinical response is defined as a reduction in the total Mayo Clinic score of at least 3 points and a decrease of at least 30% from Baseline (Week 0) to Week 52, and a reduction in the rectal bleeding subscale of at least 1 point from Baseline (Week 0) to Week 52 or an absolute rectal bleeding score of 0 or 1 at Week 52.
- Clinical remission (i.e., a total Mayo Clinic score of ≤ 2 and no subscores > 1) at Week 52;
- Durable clinical responses and durable clinical remissions at Week 52 (i.e., present at both Week 12 and Week 52), and glucocorticoid-free clinical remission at Week 52;
- Mucosal healing (i.e., an mMES of 0 or 1) at Week 52;
- Improvement in the mucosa according to the following assessments:
 - At least a 1-point improvement in the mMES from Baseline (Week 0) to Week 52;
 - A mean change in the UCEIS score from Baseline (Week 0) to Week 52; and/or
 - At least a 1-point improvement in the modified Baron endoscopic score from Baseline (Week 0) to Week 52.
- Remission (i.e., mMES of 0 or 1, stool frequency subscore of 0 or 1, and rectal bleeding subscore of 0) rates at Week 12 and Week 52;
- Improvement in the HRQL, which will be based on the subject's completed IBDQs;
- Lowered corticosteroid (glucocorticoid) dosages;
- Glucocorticoid-free treatment duration from Week 16 through Week 52, and through the OLE/LTE Therapy Follow-up Period (Week 56 through Week 64);
- PD profile of KHK4083;
- PK-PD relationships.

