12.3.3 Exploratory Efficacy Analysis

Clinical improvement (changes from Baseline [Week 0] to Week 52 in the total Mayo Clinic score) at Week 52 will be summarized. In addition, change from Baseline (Week 0) in partial Mayo Clinic scores (without sigmoidoscopy) will be summarized by study visit at Weeks 16, 20, 24, 28, 32, 36, 40, 44, 48, and 52 and at OLE/LTE Therapy Follow-up Period visits (Weeks 56, 60, and 64).

Clinical response at Week 52 will be summarized. Clinical remission will be summarized at Week 52.

At Weeks 12 and 52, durable clinical response and durable clinical remission (present at both Weeks 12 and 52), and glucocorticoid-free clinical remission at Week 52 will be summarized.

Remission (mMES of 0 or 1, stool frequency subscore of 0 or 1 and rectal bleeding subscore of 0) rates at Weeks 12 and 52 will be summarized.

The percentage of subjects with mucosal healing at Week 52 will be summarized. The percentages of subjects with improvement in the mucosa (change from Baseline of at least a 1-point improvement in the mMES and/or in the modified Baron endoscopic scores; and/or mean change from Baseline in the UCEIS score) at Week 52.

The change from Baseline in HRQL based on IBDQ will be analyzed for total score and 4 subscale scores at all study visits (Weeks 2 to 52, including Induction Therapy Follow-up Period visits (Weeks 16, 20, and 26) and LTE Therapy Follow-up Period visits (Weeks 56, 60, and 64).

At Weeks 16 through 52 and through the OLE/LTE Therapy Follow-up Period (Week 56 through Week 64), the change from Baseline in corticosteroid (glucocorticoid) dosages and the duration of glucocorticoid-free treatment will be summarized.

Treatment (each KHK4083 dose level versus placebo) comparisons by cohort and OLE/LTE will be performed with the linear model for all exploratory efficacy analyses of continuous variables.

Exploratory analyses are described in detail in the SAP.

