3.4.3 Exploratory efficacy endpoints

	Forms			
	Title	Statistical Analysis Plan Template		
	Code	Version	Effective Date	Page
	FRM_ST03_032	01	23 Apr 2015	18 of 53

Efficacy exploratory endpoints will be included in this study for all subjects with moderately active UC who receive both Induction Therapy and OLE/LTE Therapy. The exploratory endpoints for all subjects who receive both Induction Therapy and OLE/LTE Therapy are as follows:

- Clinical improvement at Week 52;
Improvement will be based on a reduction (mean change from Baseline [Week 0] to Week 52) in the total Mayo Clinic score (0 to 12).
- Clinical improvement at Weeks 16, 20, 24, 28, 32, 36, 40, 44, 48, and 52 and at OLE/LTE Therapy Follow-up Period visits (Weeks 56, 60, and 64);
Improvement will be based on mean changes from Baseline (Week 0) in the partial (excludes endoscopy subscores) Mayo Clinic score (0 to 10).
- Clinical response at Week 52;
A clinical response is defined as a reduction in the total Mayo Clinic score of at least 3 points and a decrease of at least 30% from Baseline (Week 0) to Week 52, and a reduction in the rectal bleeding subscale of at least 1 point from Baseline (Week 0) to Week 52 or an absolute rectal bleeding score of 0 or 1 at Week 52.
- Clinical remission (i.e., a total Mayo Clinic score of ≤ 2 and no subscores > 1) at Week 52;
- Durable clinical responses and durable clinical remissions at Week 52 (i.e., present at both Week 12 and Week 52), and glucocorticoid-free clinical remission at Week 52;
- Mucosal healing (i.e., an mMES of 0 or 1) at Week 52;
- Improvement in the mucosa according to the following assessments:
 - At least a 1-point improvement in the mMES from Baseline (Week 0) to Week 52;
 - A mean change in the UCEIS score from Baseline (Week 0) to Week 52; and/or
 - At least a 1-point improvement in the modified Baron endoscopic score from Baseline (Week 0) to Week 52.
- Remission (i.e., mMES of 0 or 1, stool frequency subscore of 0 or 1, and rectal bleeding subscore of 0) rates at Week 12 and Week 52;
- Improvement in the HRQL, which will be based on the subject's completed IBDQs;
- Lowered corticosteroid (glucocorticoid) dosages;
- Glucocorticoid-free treatment duration from Week 16 through Week 52, and through the OLE/LTE Therapy Follow-up Period (Week 56 through Week 64);

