7.3 Analysis of exploratory efficacy endpoints

All exploratory efficacy variables will be summarized by treatments. The changes from Baseline in mMES, UCEIS and total Mayo Clinic score as well as Baseline and Week 52 will be summarized by treatments. In addition, the partial Mayo Clinic scores (without sigmoidoscopy) and changes from Baseline will be summarized by study visit at Weeks 16, 20, 24, 28, 32, 36, 40, 44, 48, and 52 and at OLE/LTE Therapy Follow-up Period visits (Weeks 56, 60, and 64).

The change from Baseline in HRQL based on IBDQ will be analyzed for total score and 4 subscale scores at all study visits (Weeks 2 to 52, including Induction Therapy Follow-up Period visits (Weeks 16, 20, and 26) and OLE/LTE Therapy Follow-up Period visits (Weeks 56, 60, and 64).

Remission (mMES of 0 or 1, stool frequency subscore of 0 or 1 and rectal bleeding subscore of 0) rates at Week 12 will be summarized. Remission rates at Week 52 will be summarized by Double-Blind Period and OLE Therapy Period as well.

Clinical response and clinical remission will be summarized at Week 52. The percentage of subjects with mucosal healing, and the percentages of subjects with improvement in the mucosa (change from Baseline of at least a 1-point improvement in the mMES and/or in the modified Baron endoscopic scores) at Week 52 will be summarized by Double-Blind Period and OLE Therapy Period.

Durable clinical response and durable clinical remission at Week 52 will be summarized by Double-Blind Period and OLE Therapy Period. Durable clinical response and durable clinical remission at Week 52 will be defined as follows:

- Duration clinical response at Week 52 will be defined in the case that clinical response is present at both Weeks 12 and 52.
- Duration clinical remission at Week 52 will be defined in the case that clinical remission is present at both Weeks 12 and 52.

Glucocorticoid-free clinical remission at Week 52 will be summarized by Double-Blind Period and OLE Therapy Period. At Weeks 16 through 52 and through the OLE/LTE Therapy Follow-up Period (Week 56 through Week 64), the change from baseline in corticosteroid (glucocorticoid) dosages and the duration of glucocorticoid-free treatment will be summarized. Those parameters definitions are shown below.

- Glucocorticoid-free clinical remission at Week 52

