 - Change from baseline in corticosteroid (glucocorticoid) dosages at Week 16 through LTE Therapy Follow-up Period = Glucocorticoid dosages at Week 16 through LTE Therapy Follow-up Period - Baseline glucocorticoid dosages
 - Change from baseline in corticosteroid (glucocorticoid) dosages at Week 16 through OLE Therapy Follow-up Period = Glucocorticoid dosages at Week 16 through OLE Therapy Follow-up Period - Baseline glucocorticoid dosages
- Duration of glucocorticoid-free treatment will be defined as the duration that no glucocorticoid listed in Section 9.3 is used from Week 16 through Follow-up 3.
 - Duration of glucocorticoid-free treatment (days) = Date of first glucocorticoid after Week 16 visit - Date of Week 16 visit
 - If the subject received glucocorticoid on the date of Week 16 visit, the duration of glucocorticoid-free treatment for the subject is 0.

A comparison between treatments (each KHK4083 dose level versus placebo) will be performed using an ANCOVA model with changes from Baseline in UCEIS, total Mayo Clinic score and partial Mayo Clinic score at Week 52 during Double-Blind Therapy Period as dependent variables, treatment as fixed effect and baseline value as covariate. The number of subjects and the number of subjects considered in the model will be provided by treatment. The adjusted means for treatments (least squares means) and the relative 95% CIs will be presented. The difference between the adjusted means for each treatment groups from placebo (Difference in Least Squares Mean from Placebo) will be calculated with the relative 95% CI and p-value. If ANCOVA cannot be applied

	Forms			
	Title	Statistical Analysis Plan Template		
	Code	Version	Effective Date	Page
	FRM_ST03_032	01	23 Apr 2015	33 of 53

due to the issue that the parameters cannot be estimated appropriately, these analyses using ANCOVA for Week 52 will not be applied.

Means with SDs for the efficacy variables (mMES, UCEIS, total Mayo score and partial Mayo score) at all visits will be performed graphically by each treatment (e.g. Placebo, 1.0 mg/kg, 3.0 mg/kg, or 10 mg/kg) and by Double-Blind Therapy Period and OLE Therapy Period. For partial Mayo score, Means with SDs as all visits will be performed graphically by “Double-Blind Therapy Period and Double-Blind Therapy Follow-up Period” and “OLE Therapy Period and OLE Therapy Follow-up Period”. Mean changes from Baseline will also be performed in the same manner.

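### The plan sets the percentage of subjects glucocorticoid-free to Week 52 and to Week 64 as an objective, but tabulates a duration and administration counts instead of either percentage

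*SAP*

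**What the plan says.** The objective is a proportion over two windows. SAP 2.3 has "To determine the percentage of subjects who are glucocorticoid-free from Week 16 through Week 52" and continues through follow-up. Protocol section 5 has "To determine the percentage of subjects who are glucocorticoid-free from Week 16 through Week 52, and through the OLE/LTE Therapy Follow-up Period", which ends at Week 64.

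The endpoint is a duration. SAP 3.4.3 lists "Glucocorticoid-free treatment duration from Week 16 through Week 52, and through the OLE/LTE Therapy Follow-up Period", and Protocol 10.3 has the same endpoint. Both name both windows.

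The analysis sections follow the endpoint. In Protocol 12.3.3, "the change from Baseline in corticosteroid (glucocorticoid) dosages and the duration of glucocorticoid-free treatment will be summarized"; SAP 7.3 says the same.

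SAP 7.3 then defines the duration as "the duration that no glucocorticoid listed in Section 9.3 is used from Week 16 through Follow-up 3", which is one window. It is computed as the date of the first glucocorticoid after the Week 16 visit minus the date of that visit, and is 0 if one is taken on the visit day.

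SAP 7.3 also defines the number of glucocorticoid administrations from Week 16 to Week 52 and from Week 16 to Follow-up 3, set to 0 when there are none.

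The outputs in SAP 9.4 and 9.6 are Tables 14.2-3.5.1 and 14.2-3.5.2 (dosages), Tables 14.2-3.5.3 and 14.2-3.5.4 (duration) and Listing 16.2.6-3.2 (subject-level values of both).

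SAP 9.3 restricts what counts as a glucocorticoid to concomitant medications with ATC code H02AB whose administration began from Day 1.

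**The concern.** A proportion and a time to first use are different quantities, and the plan moves from one to the other without saying so. If the SAP is followed as written, the report will give summary statistics for days and for administrations, and the reader will not find the share of subjects who stayed off glucocorticoids to Week 52 or to Week 64.

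Two details of the definitions bear directly on that share:

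- **Never-users.** The duration formula needs a first-use date. Subjects who never use a glucocorticoid are the ones the objective counts, and they have no such date. No cap or censoring rule is given.
- **Background steroid.** Protocol 8.5 allows stable oral glucocorticoids begun before Screening, so some subjects may enter on them. Under a literal reading of SAP 9.3, such a subject who continues the same drug throughout has no qualifying glucocorticoid and is classed as free. The same rule feeds glucocorticoid-free remission, the dosage counts and the duration.

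**Working it through.** The documents state no figure for this objective, so there is none to reproduce. The check is a trace of the text, followed by a test of whether the planned statistics could stand in for the percentages.

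**Trace**

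| Step | Where | Quantity | Window(s) |
|---|---|---|---|
| Objective | Protocol 5, SAP 2.3 | Percentage of subjects | Week 16–52; on to Week 64 |
| Endpoint | Protocol 10.3, SAP 3.4.3 | Duration | Week 16–52; on to Week 64 |
| Definition | SAP 7.3 | Days to first use | Week 16 to Follow-up 3 |
| Definition | SAP 7.3 | Number of administrations | Week 16–52; Week 16 to Follow-up 3 |
| Tables | SAP 9.4 | Dosages and duration | by extension period with its follow-up |

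The percentage drops out at the endpoint. The separate Week 52 cut of the duration drops out at the SAP definition.

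The nearest planned percentage is glucocorticoid-free clinical remission at Week 52. It also requires remission, serves a separately listed objective, and has no Week 64 version.

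**Window lengths**

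- Week 16 to 52: (52 − 16) × 7 = 252 days.
- Week 16 to 64: (64 − 16) × 7 = 336 days.

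**Do the planned statistics fix the percentage?**

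SAP 4.1 summarizes continuous variables by n, mean, SD, median, minimum and maximum. Take nine hypothetical subjects, and assume that never-users are assigned 336 days (a cap the SAP does not state).

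- Set A: 0, 0, 0, 84, 168, 252, 252, 252, 336.
- Set B: 0, 0, 0, 168, 168, 168, 168, 336, 336.

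For both sets:

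- Sum = 1344, so mean = 1344/9 = 149.3.
- Sum of squares = 338,688, so SD = √[(338,688 − 1344²/9)/8] = √17,248 = 131.3.
- Median 168, minimum 0, maximum 336.

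Every planned statistic agrees. The percentages do not:

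- Free to Week 52 (at least 252 days): A 4/9 = 44.4%; B 2/9 = 22.2%. If use on the Week 52 day itself counts as use, A becomes 1/9 = 11.1% and B stays at 22.2%.
- Free to Week 64 (336 days): A 1/9 = 11.1%; B 2/9 = 22.2%.

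**The same test on administration counts**

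Replace each value x by 336 − x and read it as the number of administrations from Week 16 to Week 64, with baseline counts of 0 so that change equals count.

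- A gives 0, 84, 84, 84, 168, 252, 336, 336, 336.
- B gives 0, 0, 168, 168, 168, 168, 336, 336, 336.

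Both have sum 9 × 336 − 1344 = 1680, mean 186.7, SD 131.3, median 168, minimum 0 and maximum 336. The share with no administrations is 1/9 in A and 2/9 in B. The dosage summary therefore does not fix the percentage either.

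**The case against.** The strongest reply is that little is missing. The endpoint text does name both windows. Administration counts are defined over both windows with 0 for non-users, so each percentage can be derived from a planned variable or counted from Listing 16.2.6-3.2. Table shells are in a separate document (SAP 9.7) and may contain the row. Every analysis is descriptive or exploratory (Protocol 12.3.5), and the proof-of-concept decision uses 12-week data (SAP 4.5).

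All of that stands, and it limits the point to an omitted tabulation and incomplete definitions. It does not remove it: a stated objective should have its estimator, windows and handling rules in the SAP text.

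Several stronger readings are tempting and are not supported:

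- **That the trial cannot produce the percentages.** It can, from data it already plans to hold.
- **That remission is the sole steroid-related percentage planned.** Concomitant medications are tabulated by drug in Tables 14.1-3.3 and 14.1-3.4. Those tables are not confined to Week 16 onward and pool follow-up, so they do not answer the objective.
- **That matching means alone prove the summary uninformative.** SD, median, minimum and maximum are also planned and separate many cases. An example has to match on all of them, as the one above does.
- **That including follow-up is an error because any colitis treatment is then allowed.** The objective itself includes follow-up. Protocol 8.5.1 lifts a specific list on which glucocorticoids do not appear, and Protocol 8.5 already permits corticosteroid adjustment after Week 12 in both extension and follow-up.
- **That early leavers must count as not free.** That is one choice among several, and Protocol 12.6 does not substitute missing values. What is needed is a stated rule.

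**Conclusion.** The mismatch is real and minor. The objective is a percentage over two windows. The SAP text and table titles plan a duration over one window and administration counts over two, and tabulate neither percentage. The planned summary statistics do not determine them: in the constructed example, identical summaries are compatible with 44.4% or 22.2% free to Week 52, and 11.1% or 22.2% to Week 64. Those figures show that the percentages are not determined; they do not forecast this trial. They assume nine subjects and a 336-day value for never-users.

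Two gaps in the definitions would affect the percentages even if someone derived them. The duration has no stated value for never-users. Section 9.3, read literally, lets background steroid use pass as glucocorticoid-free. The second depends on that literal reading: a programmer might take the sentence to mean any use from Day 1 onward, which is why the wording needs settling.

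The finding rests on the SAP text and titles, because the shells are not available. It touches one exploratory, descriptive objective and no decision that the documents describe.

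**What to change.** - In SAP 7.3 and Tables 14.2-3.5.3 and 14.2-3.5.4, add the number and percentage of subjects entering OLE/LTE with no glucocorticoid use from Week 16 through Week 52 and, separately, through Week 64.
- Amend SAP 9.3 so that a glucocorticoid ongoing from before Day 1 counts as use. Apply the amended rule to glucocorticoid-free remission, dosages and duration as well, so that the results agree.
- State the denominator, how subjects who leave before the end of a window are handled, and in which table a subject who moves from LTE to OLE (possible up to Week 28) is counted.
- Give the duration a value or a censoring rule for subjects with no use.
- Align the endpoint wording in SAP 3.4.3 with the objective in 2.3.
- Optionally, repeat the rows for subjects on glucocorticoids at Day 1. The objective does not ask for this.

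The cost is SAP wording, a few rows in two planned tables, and reprogramming of the variables that use Section 9.3. Concomitant medications are already recorded at every visit (Protocol Tables 9-1 and 9-2), so no new data are needed.
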